## Study protocol

### Participants

Healthy adults (n = 18, age 19-35, 9 males and 9 females) who were recreationally active volunteered to participate in this study. Exclusion criteria included 1) any cardiovascular, neurological, metabolic, respiratory, or renal diseases, 2) any musculoskeletal conditions or injuries, 3) presence or history of stomach ulcers, 4) prescribed medications or over-the-counter medications, 5) pregnant, trying to become pregnant, or breast-feeding women, 6) any history of smoking/current smoker, and 7) any allergies to fruits or vegetables. The procedures used in this study were approved by the Institutional Review Board at the University of Nebraska Medical Center and carried out in accordance with the Declaration of Helsinki. All participants gave their written informed consent prior to study enrollment, during which the experimental procedures, potential risks, and potential benefits were explained. This study was registered with <https://clinicaltrials.gov/> (NCT04312022).

### Study design

A randomized, double-blind, placebo-controlled, crossover study design with a 2-week washout period was used. After study enrollment, participants were randomly assigned to either the BE supplement group or the placebo control group. All data collections were performed at the same time of day ( $\pm 1\text{h}$ ) after an overnight fast, and participants were asked to abstain from caffeine, alcohol, high intake of antioxidant-rich foods or supplements, and excessive exercise for at least 48 hours prior to their visits. Participants were also informed to not change their dietary habits during the study period. Descriptive measurements of height, weight, BMI, body composition, and hand grip strength were taken at both BE and placebo visits. Baseline measurements of RHR, BP, blood sampling for TAC, endothelial function, skeletal muscle oxygen utility capacity during exercise, and muscular fatigue index were assessed. Participants then consumed either the BE or placebo, and all baseline measures were repeated as experimental measures 1 hour after BE or placebo intake. A 1-hour digestion period was chosen because anthocyanins have been shown to reach peak levels in the blood within 1-hour post consumption. After 2 weeks each participant returned for a second visit and the same protocol was repeated with the intervention (BE or placebo) they did not receive in the first visit. All women (n = 9) were tested during the early-to-mid follicular (days 1 – 10) and late-luteal phases (> day 19) of the menstrual cycle in order to avoid confounding effects of endogenous estrogen on autonomic function.

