#### Endothelial function

Flow-mediated dilation (FMD) of the brachial artery was used to assess endothelial function before and after BE and placebo intake. FMD is an endothelium-dependent assessment that facilitates brachial artery relaxation in response to an increase in shear stress. FMD was assessed using a Terason uSmart 3300 Doppler ultrasound system (Terason Division Teratech Corporation, Burlington, MA) and EKG trigger

monitor (7700 Series Trigger Monitor, IvyBiomedical Systems, Inc., Branford, CT). The ultrasound probe was used to locate the brachial artery on the participant's right arm, and a rapid-inflation cuff (E20 Rapid Cuff, D.E. Hokanson, Bellevue, WA) was placed on the forearm distal to the ultrasound probe. A baseline resting brachial artery diameter was recorded for 5 minutes using an image capturing system (Vascular Imager, Vascular Research Tools 6, Medical Imaging Applications, Coralville, IA). The cuff was then inflated to 250 mmHg for 5 minutes. The cuff was released, and the reactive hyperemic response of the artery was recorded for 5 minutes using the ultrasound and image capturing system. The baseline resting diameter and post-hyperemic stimulus were analyzed using automated edge detection software (Brachial Analyzer, Vascular Research Tools 6, Medical Imaging Applications, Coralville, IA). The most stable 30-60 seconds of the baseline artery diameter measurement, including at least 10 cardiac cycles, was averaged as the resting diameter.

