#### Skeletal muscle oxygen utility capacity

Skeletal muscle oxygen utility capacity during single leg extension exercise was assessed before and after BE and placebo intake. Oxygenation utility capacity of the vastus lateralis was measured during leg extension exercise with a commercially available NIRS system (Artinis PortaMon, Einsteinweg, The Netherlands). The PortaMon emits near-infrared wavelengths of 850 and 764 nm and has a detection probe to measure returning signals, and data were recorded continuously at 10 Hz to quantify tissue saturation index (StO2, %) and concentrations of both oxygenated hemoglobin ([O2Hb], a.u.) and deoxygenated hemoglobin ([HHb], a.u.).

To determine single leg extension strength, a 1-repetition maximum (1RM) test was performed using the participant's dominant leg. Participants were familiarized with the leg extension technique before the 1RM measurement, which was achieved within 3 attempts. The 1RM was considered the highest weight that could be lifted in good form through a full range of motion. The PortaMon was secured with a commercially available, double-sided adhesive at one- third of the distance from the lateral femoral epicondyle and the greater trochanter, and the device was adjusted to be on the belly of the vastus lateralis muscle. The device was wrapped in black, light-absorbing cloth to reduce extraneous light that may affect the signals. Participants were then asked to perform 15 repetitions at 60% of their 1RM while NIRS data were recorded continuously throughout the exercise protocol.

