#### Fatigability index

Fatigability index was quantified during Isokinetic contraction of the participant's dominant leg before and after BE and placebo intake using HUMAC NORM Isokinetic Dynamometer (CSMi Solutions, Stoughton, MA). The participants were seated upright with the axis of rotation of the dynamometer arm oriented with the axis of rotation of the participant's dominant knee. Belts and straps were used to secure the participant to the dynamometer, and participants were instructed to fully extend and flex their knee and to work to their maximal capacity during the leg extension exercise. Before the test, there were 4 familiarization repetitions at the testing resistance. The testing consisted of a mild resistance at 240°/sec to induce and measure muscular fatigue. The software (HUMAC 2015, v.15.000.0103) reported the data of fatigue index, which was calculated using the percentage peak torque differences that were

found on the first and final 5 repetitions of the exercise bout (fatigue index = [initial peak torque – final peak torque]/initial peak torque \* 100). The data obtained from the analysis software allowed for the assessment of changes in numbers relative to the participant baseline measurements.

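### Leg exercise before the dose means post-dose FMD, RHR, BP and TAC describe a recently exercised state: the BE-placebo contrast stays valid, but its conclusion must be limited to that state and within-BE pre/post tests avoided

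*Combined protocol and SAP*

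**What the plan says.** All references are to the combined protocol and SAP.

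- **Order of events (Study design).** The baseline list starts with RHR, BP, the blood draw for TAC and endothelial function, and ends: "skeletal muscle oxygen utility capacity during exercise, and muscular fatigue index were assessed. Participants then consumed either the BE or placebo". After the capsules, "all baseline measures were repeated as experimental measures 1 hour after BE or placebo intake".
- **Design (Study design).** "A randomized, double-blind, placebo-controlled, crossover study design with a 2-week washout period was used". At the second visit "the same protocol was repeated with the intervention (BE or placebo) they did not receive in the first visit".
- **Exercise before visits (Study design).** Participants were asked to abstain from "excessive exercise for at least 48 hours prior to their visits". Nothing is said about exercise within the visit.
- **Leg tests.** Under Skeletal muscle oxygen utility capacity, participants do 15 repetitions at 60% of 1RM before and after intake. In addition, "a 1-repetition maximum (1RM) test was performed using the participant's dominant leg"; when, and at which sessions, is not stated. Under Fatigability index, the isokinetic test is also done before and after intake. It uses mild resistance at 240°/sec, but participants are told "to work to their maximal capacity during the leg extension exercise".
- **Resting measures.** RHR and BP follow five minutes of seated rest and are recorded as resting values. For FMD, "The baseline resting diameter and post-hyperemic stimulus were analyzed using automated edge detection software". Neither section sets a recovery period after the leg tests.
- **Analysis (Statistical analysis).** A 2 × 2 repeated measures ANOVA (group by time), with paired t-tests after any significant effect, not only after a significant interaction. The sample size rests on FMD: at least 16 participants, 80% power, a 3 to 5% change between the two groups.

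**The concern.** Every post-dose RHR, BP, TAC and FMD value follows leg exercise done earlier in the same visit. That is true whatever the order of tests within a battery, and whether or not the 1RM was part of each visit. If the tests were run in the order listed, the pre-dose values of the same four outcomes are rested. The change from before to after intake then contains the supplement, the exercise and the passage of time together.

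Two things are at stake.

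1. **What the trial can claim.** The BE-placebo contrast is an effect of BE in people who have recently exercised. If exercise dampens or enhances the effect of BE, the rested-state effect is a different number, and the trial cannot recover it.
2. **Which comparison is read.** A before-after difference within the BE condition could be reported as a supplement effect when exercise or time produced it.

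FMD needs particular care. On the usual percent-change formula it is divided by the resting diameter, so a shift in that diameter can move FMD even when peak diameter does not change.

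**Working it through.** **1. The plan's own figure.** N = 16 cannot be reproduced, because no SD or within-subject correlation is given. Back-solving with a two-sided paired t-test (alpha 0.05, n = 16, 80% power) gives a standardised difference of 0.749. Reading the target as FMD points, which the plan does not say, the implied SD of the paired difference is 3/0.749 = 4.0 to 5/0.749 = 6.7 points.

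**2. What each comparison estimates.** Let μ be the pre-dose mean, t the time effect, e the exercise effect, and s the BE effect in the exercised state. Period and carry-over are left out.

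| Cell | Mean |
|---|---|
| Pre-dose, either visit | μ |
| Post-dose, placebo | μ + t + e |
| Post-dose, BE | μ + t + e + s |

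- Group × time contrast: (t + e + s) − (t + e) = s.
- Post-dose BE minus post-dose placebo: s.
- Within-BE post minus pre: t + e + s.
- Time main effect, averaged over conditions: t + e + s/2.

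The shared exercise effect cancels from the first two and stays in the last two.

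**3. Error rates with no supplement effect.** Simulation, n = 18, 20,000 replicates per setting. Assumed: between-subject SD 2 FMD points; residual SD σ of 1.5 or 2.0; a participant-specific exercise shift, the same at both visits, with the mean below and SD 1 (no shift at all in the first row).

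| Mean shift (FMD points) | Group × time | Post-dose BE vs placebo | Within-BE pre/post | Time main effect |
|---|---|---|---|---|
| 0 | 5.0–5.2% | 5.0–5.1% | 5.0–5.2% | 4.9% |
| −1 | 5.1% | 4.8–4.9% | 27–40% | 44–60% |
| −2 | 5.1% | 4.9% | 76–93% | 95–99% |
| −3 | 5.1–5.2% | 5.0% | 98–99.9% | 100% |

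Bias in the group × time contrast was below 0.01 points throughout. The time main effect matters because, under the plan's wording, it alone is enough to open the paired t-tests.

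**4. If exercise modifies the BE effect.** Assume a rested effect of 3 points, an SD of the difference of 4.0 (from step 1) and n = 18. The estimand is 3 × multiplier.

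| Multiplier | Effect estimated | Power |
|---|---|---|
| 0.5 | 1.5 | 32% |
| 0.75 | 2.25 | 61% |
| 1 | 3 | 85% |
| 1.25 | 3.75 | 96% |
| 1.5 | 4.5 | 99% |

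**5. Sensitivity of FMD to resting diameter.** Formula assumed: (peak − resting)/resting. Diameters assumed: 4.00 mm resting and 4.28 mm peak, so 0.28/4.00 = 7.0%.

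| Resting diameter | Peak fixed at 4.28 mm | Dilation fixed at 0.28 mm | Dilation proportional |
|---|---|---|---|
| 4.08 mm (+2%) | 0.20/4.08 = 4.9% | 0.28/4.08 = 6.9% | 7.0% |
| 4.12 mm (+3%) | 0.16/4.12 = 3.9% | 0.28/4.12 = 6.8% | 7.0% |

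The shift is 2.1 to 3.1 points with a fixed peak, 0.1 to 0.2 points with fixed dilation, and zero with proportional dilation.

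**The case against.** The strongest reply is that the crossover already deals with this. The same people do the same exercise at both visits, and the planned model contains the group × time term. That stands. A reader might infer that prior exercise confounds the supplement effect, or that the trial fails to isolate one. Steps 2 and 3 show otherwise: a shift shared by both visits leaves the randomised contrast unbiased, with its error rate at about 5%.

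Other parts of the reply also stand:

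- The available text states no objective of resting vascular function. The word resting is attached only to the RHR and BP values and to the artery diameter.
- The exercise is brief and mostly single-leg, and the isokinetic resistance is described as mild. The documents do not say how large its effect on FMD, RHR, BP or TAC is, or how long it lasts.
- The 2.1 to 3.1 point figure is the least favourable of three cases. It describes a change within a visit, whereas the planning target is a difference between conditions. A diameter change common to both visits largely drops out of that difference.
- The pre-dose leg tests have a purpose. The Fatigability index section assesses change from the participant's own baseline, and the NIRS haemoglobin signals are in arbitrary units from a probe placed afresh two weeks apart.

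The reply leaves two gaps. It does not show that exercise leaves the effect of BE unaltered, and it does not protect the within-BE tests that the plan allows.

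**Conclusion.** The point holds as a limit on the estimand and on which comparisons may be read as supplement effects. The BE-placebo contrast is sound, but it is the effect of BE after prior leg exercise. Extending it to a rested state requires that exercise does not modify the effect, and nothing in the documents supports that. The reverse inference, that a null result shows exercise masked an effect, is equally unsupported: modification is possible but not documented.

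Within-BE pre/post tests do not identify a supplement effect. Under the assumed shifts of −1 to −3 points they reject in 27% to 99.9% of trials with no effect present.

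All sizes here rest on assumed shifts, SDs, multipliers and diameters. That the post-dose values follow exercise is firm. That the pre-dose values are rested depends on the listed order having been the order of testing. The 1RM should not be counted as part of each pre-dose battery, since its timing is not given.

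**What to change.** 1. **Inference and wording.** For FMD, RHR, BP and TAC, base supplement conclusions on the group × time (BE-placebo) contrast and state them as effects after prior leg exercise. Do not let a time main effect or a within-BE paired test carry a supplement claim. Report the order of tests, when the 1RM was done, and the interval between the leg tests and the post-dose measures. Cost: wording, and a narrower conclusion.
2. **Resting diameter.** Report resting brachial diameter as its own outcome. Add a supportive FMD analysis of log peak diameter adjusted for log resting diameter, using diameters from the edge-detection software. Treat it as a sensitivity analysis, not as a condition the FMD claim must meet. Cost: a little analysis time on existing data.
3. **Optional, for future work only.** The documents are written in the past tense, so visit order may no longer be open to change. A later trial could run the leg tests only after the post-dose resting measures, at the price of the same-day leg baseline. With equal variances and a common between-visit correlation rb, the difference in changes has variance 4s²(1 − rw), where rw is the within-visit correlation, and the post-only difference has 2s²(1 − rb). Post-only is more precise unless rw exceeds (1 + rb)/2; for example, 0.80 when rb is 0.6. Neither correlation is given, so this is a trade-off and not a required change.

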### Supplementation

The antioxidant supplement used in this study contained 3 natural plant-based ingredients including 1) hawthorn berry extract, derived from the hawthorn berry (*Crataegus spp.*), 2) tart cherry powder (*Prunus cerasus*), a rich source of anthocyanins, and 3) bromelain, a mixture of proteases obtained from the stems and immature fruits of pineapples. The BE supplement consisted of 2 capsules with a total of 465mg, 480mg, and 400mg of hawthorn extract, tart cherry powder, and bromelain, respectively (CardioEffects, Fitfully LLC, Omaha, NE, USA). This is similar to other doses used in previous studies and has been shown to have no adverse side effects. The anthocyanin content for this supplement was provided by the company, in which two capsules contain ~68 mg of anthocyanins. The separate

components include ~67 mg from tart cherry and ~2000 ng from hawthorn berry, which is consistent with previous studies. The tart cherry anthocyanin content is similar to ~31 mL of tart cherry juice while the hawthorn berry anthocyanin content is similar to ~1g of dried hawthorn berries. Bromelain is primarily extracted from pineapple stems, and therefore bromelain is more often given in supplement form than by natural consumption. All capsules used in the present study came from the same batch from the manufacturer. The placebo consisted of 2 tapioca powder capsules that were identical in size and appearance to the BE supplement and did not possess any antioxidant properties. The capsules were given to the participant by a lab member not directly involved in the study measurements or analyses.

#### Anthropometrics

A standard stadiometer was used to measure height to the nearest 0.1 cm. Body mass was measured to the nearest 0.1 kg using a standard scale. Body mass index (BMI) was calculated as the body mass divided by the square of height (kg/m^2). Body fat percentage was quantified using handheld bioelectrical impedance analysis (BIA) (Omron, model HBF-306C, Omron Healthcare, Inc., Lake Forest, IL). Body fat percentage was measured in duplicate, and the average of the 2 was recorded as the body fat percentage.

#### Resting heart rate and blood pressure

RHR and BP were assessed before and after BE and placebo intake. Participants rested in a seated position in a quiet room for 5 minutes and were informed not to talk or move during this time. RHR, systolic BP, and diastolic BP were measured using an automated sphygmomanometer (Omron Blood Pressure Monitor BP786N, Omron Healthcare, Inc., Lake Forest, IL) in duplicate. The two measurements of the RHR and BP were averaged and recorded as the resting values.

#### Blood sampling

Blood samples were collected from an antecubital vein by a trained phlebotomist using EDTA tubes before and after BE and placebo intake. Samples were centrifuged at 3500 rpm for 10 minutes at 4°C. Plasma samples were stored at -30°C for later analysis of total antioxidant capacity (TAC). TAC was assessed using a commercially available Total Antioxidant Capacity Assay Kit (CAT#: ab65329, Abcam, Cambridge, UK) according to the manufacturer's instructions. After incubating samples at room temperature (23°C), absorbances were measured at 570nm using a microplate reader. The average intra-assay and inter-assay coefficient of variation for TAC were 6.3% and 2.9%, respectively.

#### Endothelial function

Flow-mediated dilation (FMD) of the brachial artery was used to assess endothelial function before and after BE and placebo intake. FMD is an endothelium-dependent assessment that facilitates brachial artery relaxation in response to an increase in shear stress. FMD was assessed using a Terason uSmart 3300 Doppler ultrasound system (Terason Division Teratech Corporation, Burlington, MA) and EKG trigger

monitor (7700 Series Trigger Monitor, IvyBiomedical Systems, Inc., Branford, CT). The ultrasound probe was used to locate the brachial artery on the participant's right arm, and a rapid-inflation cuff (E20 Rapid Cuff, D.E. Hokanson, Bellevue, WA) was placed on the forearm distal to the ultrasound probe. A baseline resting brachial artery diameter was recorded for 5 minutes using an image capturing system (Vascular Imager, Vascular Research Tools 6, Medical Imaging Applications, Coralville, IA). The cuff was then inflated to 250 mmHg for 5 minutes. The cuff was released, and the reactive hyperemic response of the artery was recorded for 5 minutes using the ultrasound and image capturing system. The baseline resting diameter and post-hyperemic stimulus were analyzed using automated edge detection software (Brachial Analyzer, Vascular Research Tools 6, Medical Imaging Applications, Coralville, IA). The most stable 30-60 seconds of the baseline artery diameter measurement, including at least 10 cardiac cycles, was averaged as the resting diameter.

#### Skeletal muscle oxygen utility capacity

Skeletal muscle oxygen utility capacity during single leg extension exercise was assessed before and after BE and placebo intake. Oxygenation utility capacity of the vastus lateralis was measured during leg extension exercise with a commercially available NIRS system (Artinis PortaMon, Einsteinweg, The Netherlands). The PortaMon emits near-infrared wavelengths of 850 and 764 nm and has a detection probe to measure returning signals, and data were recorded continuously at 10 Hz to quantify tissue saturation index (StO2, %) and concentrations of both oxygenated hemoglobin ([O2Hb], a.u.) and deoxygenated hemoglobin ([HHb], a.u.).

To determine single leg extension strength, a 1-repetition maximum (1RM) test was performed using the participant's dominant leg. Participants were familiarized with the leg extension technique before the 1RM measurement, which was achieved within 3 attempts. The 1RM was considered the highest weight that could be lifted in good form through a full range of motion. The PortaMon was secured with a commercially available, double-sided adhesive at one- third of the distance from the lateral femoral epicondyle and the greater trochanter, and the device was adjusted to be on the belly of the vastus lateralis muscle. The device was wrapped in black, light-absorbing cloth to reduce extraneous light that may affect the signals. Participants were then asked to perform 15 repetitions at 60% of their 1RM while NIRS data were recorded continuously throughout the exercise protocol.

#### Fatigability index

Fatigability index was quantified during Isokinetic contraction of the participant's dominant leg before and after BE and placebo intake using HUMAC NORM Isokinetic Dynamometer (CSMi Solutions, Stoughton, MA). The participants were seated upright with the axis of rotation of the dynamometer arm oriented with the axis of rotation of the participant's dominant knee. Belts and straps were used to secure the participant to the dynamometer, and participants were instructed to fully extend and flex their knee and to work to their maximal capacity during the leg extension exercise. Before the test, there were 4 familiarization repetitions at the testing resistance. The testing consisted of a mild resistance at 240°/sec to induce and measure muscular fatigue. The software (HUMAC 2015, v.15.000.0103) reported the data of fatigue index, which was calculated using the percentage peak torque differences that were

found on the first and final 5 repetitions of the exercise bout (fatigue index = [initial peak torque – final peak torque]/initial peak torque \* 100). The data obtained from the analysis software allowed for the assessment of changes in numbers relative to the participant baseline measurements.

